randomized to ET will be given a stationary foot peddler. Participants randomized to CT+ET will start with CT (tablet based brain games) followed by ET after a 15 minute break. We will administer the interventions for six months. The primary outcome is change in executive function measured by the Trailmaking Test A and B (TMTA/B) scores between enrollment and 3 months of intervention. Global cognitive function will be a secondary cognitive outcome and will be assessed using the Montreal Cognitive Assessment (MoCA). Changes in secondary cognitive outcomes between baseline and 3 months will be studied. We will also consider the 6-month change in all global cognitive function and executive function as a secondary outcome. The findings from this RCT will provide nephrologists who care for this vulnerable population with the first feasible and effective interventions for their patients who are at risk for experiencing executive function decline.

Objectives

Primary Objective: The primary objective is to determine if receiving CT, ET, or CT+ET preserves executive function relative to those with SC.

Secondary Objectives: The secondary objectives are to compare the rates of secondary cognitive outcomes, ESRD-specific clinical outcomes and patient-centered outcomes among those receiving CT, ET, or CT+ET relative to those in SC.

Background and Significance

Cognitive decline is a growing concern not only in the general population but also among patients undergoing dialysis. The consequences of this cognitive decline are profound and impact morbidity and mortality. Through this study, we hope to identify interventions to preserve cognitive function and develop implementation tools to help disseminate these interventions to dialysis centers nationally.

In a survey we conducted of 101 HD patients, the activities most reported during HD were watching TV (87%), talking (76%), and sleeping (67%). Ninety-five percent participated in passive activities, and <1% reported exercising while on dialysis. The time spent on HD may be a missed opportunity to improve the health of ESRD patients.

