Exercise Peddlers: Foot peddlers will be disinfected with an EPA registered tuberculocidal "hospital disinfectant" or 1:100 dilution of bleach (300-600 mg/L free chlorine). Foot peddlers will be disinfected following the same protocol outlined for iPads/tablets.

Baseline Assessments: After establishing eligibility, a research assistant will perform a baseline assessment for each participant at each center. Our trained research assistants will assess physical function, Health Related Quality of Life (HRQOL), frailty status, patient-centered outcomes, and executive and global cognitive function at enrollment. These scales have been studied and validated in ESRD (92-97). The baseline assessment consists of 2 parts: a survey/questionnaire and in-person assessments. The survey will take 15-20 minutes to complete and will be done by phone on the participant's non-dialysis day. The in-person assessments will be 30-40 minutes in duration and will allow us to establish a relationship with each participant. We will abstract demographics, health behaviors, medical information, clinical measures, and dialysis factors from each participant's medical record. We will also ask participants about previous cognitive training within the last 6 months. All in-person baseline and follow-up assessments will be administered prior to dialysis initiation as executive function fluctuates during and immediately after HD (11, 98).

Table 2: Assessments Measured at Baseline and at 3- and 6-Month Follow-up (*Only at baseline)

Assessment	Collection Method	Assessment Tool	Timing of Assessment
Physical function	Direct measurement	IADL/ADL, Short Physical Performance Battery (SPPB): walk speed, chair stands, and balance (99-102)	Baseline and at 3- and 6-month Follow-up
Executive function	Direct measurement	Trail Making Test A and B (TMTA/B) (5), Stroop (103), and Digit Symbol Substitution Tests (104)	Baseline and at 3- and 6-month Follow-up
Global cognitive function	Direct measurement	MoCA (106)	Baseline and at 3- and 6-month Follow-up
Memory	Direct measurement	Auditory/Verbal Learning Test	Baseline, at 3- and at 6-month follow up
Frailty	Direct measurement	Fried Frailty Phenotype (107): low physical activity, unintentional weight loss, poor grip strength, slowed walk speed, exhaustion	Baseline and at 3- and 6-month Follow-up
Quality of life	Validated survey	Kidney Disease Quality of Life (KDQOL) (108-110)	Baseline and at 3- and 6-month Follow-up

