Follow-up Assessments: We will perform follow-up assessments at 3 months of intervention and 6 months of intervention (measures listed in Table 2) in the dialysis center using a similar approach to the baseline assessment for comparability of the measures. Research assistants blinded to the assigned study arm will perform follow up assessments.

The Principal Investigator/ Program Manager will inform the appropriate dialysis center treating nephrologist/nurse practitioner of any abnormal findings for cognitive function, anxiety, and depression at the 3 month and 6 month assessments.

Data collection for variables needed for DSMB review. Falls during the intervention or assessment will be directly observed by study staff at each intervention session throughout the whole study. Hypotension (SBP<110 mmHg or DBP<50 mmHg) and hypertension (SBP>150 mmHg or DBP>90 mmHg) will be identified during the clinical measurements of blood pressure that occur approximately 10 times throughout the dialysis session. Similarly elevated heart rate (>80% of maximum heart rate calculated as 220-participant age will be identified during the clinical measurements of heart rate that occur approximately 10 times throughout the dialysis session. Cramping and headaches will be noted if a participant tells the study staff that they are experiencing these events. Injurious falls for DSMB review outside of the dialysis session will be self-reported by participants as part of the questionnaire at 3- and 6-months follow-up.

Plan for Fidelity Monitoring. In the pilot study, there was a small dropout rate (3/23), which is consistent with other intradialytic exercise interventions at 6 months (86) and there is high compliance (88%) with ET (63). We will allow for temporary noncompliance due to acute illness or travel. We will add additional sessions onto the end of the intervention period (no more than 2 weeks) in any of the study arms, as has previously been proposed in intradialytic intervention trials (86). The Program Manager/Study Coordinator

will visit the dialysis centers administering these arms of the study monthly throughout the course of the intervention to give a refresher on the safe and effective use of the foot peddlers. The PI or project manager will visit each clinic weekly during the administration of the intervention to directly observe compliance and facilitate communication among the HD clinic staff, patients, and study staff. Research assistants will record the:

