Based on the pilot study we assumed an 88% consent rate per arm; this will leave approximately 57-60 participants from which we will need to recruit 50 per arm. We also accounted for 6% attrition in 3 months.

1.1. Change in Secondary Measures of Cognitive Function Over 6 Months. We will use a linear mixed model approach to describe the 3- and 6-month change in secondary cognitive function measures. We will construct a base model by fitting a single slope after enrollment. We will include two random effects: intercept and time relative to enrollment. This will allow for a unique trajectory for each participant, which varies randomly around the trajectory described by the fixed effects. The estimate for the time since enrollment variable will quantify the magnitude of the change in executive and global cognitive function (pre- and post-intervention) associated with CT, ET, and CT+ET. We will explore non-linear functions of time through cubic splines. The model is:

$$(CF_{ij} - CF_{i0}) = [\beta_{00} + \beta_{1i} \text{time}_{ij} + \beta_{01} X_i + \beta_{11} X_i (\text{time}_{ij})] + [b_{0i} + b_{1i} (\text{time}_{ij})] + r_{ij} + \varepsilon_{ij}$$

where time is time since enrollment, and X is the vector of interventions. We recognize that mortality may occur during the study and those who are survivors may be a distinct population and there may be differential mortality by intervention. If we find evidence for this differential survival, we will account for the unobservable executive and global cognitive function after death by 1) creating a composite endpoint that ranks mortality as worse than any change in executive or global cognitive function (composite endpoint), and 2) generate a causal model for change regardless of mortality using a survival-averaged causal effect model. As a sensitivity analysis, we will test that our findings are robust to the analytic approach using global z-scores.

2.0. Analytic Methods: Effect of CT, ET, and CT+ET on ESRD-specific clinical outcomes.

Staff at NYU Langone Health will help with data analysis. Data will be shared through a HIPAA Compliant Johns Hopkins REDCap database. The NYU Langone Health team will be conducting data analysis for all components of this study and requires all variables to do so.

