2.1. Time to Event Outcomes: Mortality. To examine the univariate association between study arm and mortality, separate product-limit estimated cumulative incidence curves will be calculated. Next, we will use a Cox proportional hazards model to estimate the association of study arm with time to the development of mortality. Censoring will occur at loss to follow-up or KT. The hazard function for the Cox model is:

$$\lambda(t|X_i) = \lambda_0(t) \exp(X_i \beta)$$

where x_i is the value of the covariate X for the i th participant, and $\lambda_0(t)$ is the baseline hazard function. If the proportional hazards assumption is not met, we will include an interaction with time.

2.2. Dichotomous Outcomes: Poor Lower Extremity Function, poor HRQOL, return to work, and amputation. We will test whether the study arm is associated with poor lower extremity function, poor HRQOL, return to work, and amputation using logistic regression or a modified Poisson regression (145), if the outcome is $>10\%$.

2.3. Count Outcomes: Number of Falls and Hospitalizations. We will use Poisson regression to test whether the study arm is associated with the number of falls and hospitalizations within the 3 months of the intervention.

3.0. Analytic Methods: Effect of CT, ET, and CT+ET on patient-centered outcomes.

Change in Patient-centered Outcome: For each patient-centered outcome, we will calculate a score. We will treat each patient-centered outcome as continuous and will estimate the change in these outcomes between baseline and 3 months. We will analyze each patient-centered outcome separately. We will analyze the change in these outcomes using the analytic plan described in 1.0.

3.1. Change in Patient-centered Outcome over 6 Months. Patient-centered outcomes are longitudinal data (3 and 6 months) and analyzed using the analytic plan described in 2.0 for repeated measures of executive function.

4.0. Treatment Effect Heterogeneity. Frailty has been associated with worse trajectories of executive function in older adults (146) and HD patients (16). Therefore, we will explore treatment heterogeneity between those who are frail and nonfrail in all primary and secondary outcomes. We will include an interaction term between frailty status and intervention type (study arm) to assess difference in treatment effect by frailty status. Using a similar approach, we will test for treatment effect heterogeneity by age, sex, and race/ethnicity.

Risks:

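### The mixed model in section 1.1 has more variance parameters than two change scores can identify, and its time slope misses any benefit already gained by month 3; the arm contrasts themselves remain estimable

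*Combined protocol and SAP*

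**What the plan says.** The opening summary of the protocol makes later change a secondary outcome: "We will also consider the 6-month change in all global cognitive function and executive function as a secondary outcome". Section 1.1 of the Statistical Methods gives the method: "We will use a linear mixed model approach to describe the 3- and 6-month change in secondary cognitive function measures". It continues: "We will construct a base model by fitting a single slope after enrollment", then "We will include two random effects: intercept and time relative to enrollment", and later "We will explore non-linear functions of time through cubic splines".

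The displayed equation has change from baseline as its response. It contains arm terms, a time slope and arm-by-time terms, a person-level intercept and slope, and two person-by-visit errors, r and epsilon. The text says that the estimate for time since enrollment will quantify the change associated with the interventions. It states no covariance structure for the random effects, does not distinguish r from epsilon, and gives neither spline knots nor a fallback.

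The visits are fixed under Follow-up Assessments: "We will perform follow-up assessments at 3 months of intervention and 6 months of intervention". Table 2 agrees ("Assessments Measured at Baseline and at 3- and 6-Month Follow-up").

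Section 3.1 sends the patient-centered outcomes at 3 and 6 months to a repeated-measures plan in section 2.0. No such plan is there; the only one is in 1.1. The statistical update at the end of the document describes analyses of 3-month change only. It neither mentions nor withdraws section 1.1, section 3.1 or the 6-month outcomes.

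**The concern.** Change from baseline is zero for everyone at enrollment, so only the 3- and 6-month values carry information. Two values per person are too few for a random intercept, a random slope and two residuals, and too few for a curve in time. An analyst following section 1.1 literally may get no convergence, or may have to choose after seeing the data which variance term to drop.

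The choice of estimand is a second problem. If the time slope is read as the intervention effect, the model answers a question about months 3 to 6, not about change since enrollment. At stake is the pre-specification and reading of the 6-month secondary results.

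**Working it through.** The plan states no figure for this point, so there is none to reproduce. The check compares what the model asks for with what the visits supply.

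**Inputs.** Response: change from baseline (equation in 1.1). Times: t = 3 and 6 months (Follow-up Assessments, Table 2). Random effects: intercept variance v0, slope variance v1, covariance c (structure not stated). Errors: variances vr and ve, with sum s.

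**Implied covariance of the two change scores.**
- V11 = v0 + 6c + 9·v1 + s
- V12 = v0 + 9c + 18·v1
- V22 = v0 + 12c + 36·v1 + s

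These three moments are all the data supply about the variance structure. The rank is that of their derivatives with respect to the parameters.

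| Structure | Parameters | Rank |
|---|---|---|
| Correlated random effects, r and epsilon | 5 | 3 |
| Independent random effects, r and epsilon | 4 | 3 |
| Correlated random effects, one residual | 4 | 3 |
| Independent random effects, one residual | 3 | 3 |
| Random intercept only, one residual | 2 | 2 |

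The first two rows are the model as written.

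**Example.** Three valid parameter sets give V11 = 20, V12 = 12, V22 = 24:
- s = 1, v0 = 51, v1 = 2, c = -25/3: V11 = 51 - 50 + 18 + 1; V12 = 51 - 75 + 36; V22 = 51 - 100 + 72 + 1.
- s = 5, v0 = 31, v1 = 10/9, c = -13/3: V11 = 31 - 26 + 10 + 5; V12 = 31 - 39 + 20; V22 = 31 - 52 + 40 + 5.
- s = 9, v0 = 11, v1 = 2/9, c = -1/3: V11 = 11 - 2 + 2 + 9; V12 = 11 - 3 + 4; V22 = 11 - 4 + 8 + 9.

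The data cannot choose among intercept variances of 51, 31 and 11.

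**The two errors.** vr and ve enter only through s, so neither sample size nor visit timing can separate them.

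**Adding a baseline row.** The change there is always 0, which would require v0 + s = 0. That contradicts the random intercept and the residuals.

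**Splines.** At t = 3 and 6, a 3-knot restricted cubic spline (with intercept) has 3 columns and rank 2; a 4-knot spline has 4 columns and rank 2. Only a straight line can be estimated.

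**Arm means.** Intercept, time, three arm terms and three arm-by-time terms make 8 columns of rank 8, for 4 arms × 2 visits = 8 cells. Every cell mean is free.

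**What the slope measures.** Let D3 and D6 be an arm's differences from standard of care in change from baseline. The arm-by-time slope is (D6 - D3)/3 per month, and the arm term is D3 - 3 × slope = 2·D3 - D6. If D3 = D6 = d, the slope is 0 and the whole benefit d sits in the arm term.

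**When a simplification changes standard errors.** With independent random effects and one residual, V22 - V11 = 27·v1, so v1 = (V22 - V11)/27. If the 6-month variance is the smaller, v1 is held at 0 and the fit forces V11 = V22. A random intercept alone always forces this.

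**Scatter in visit dates (assumption).** Suppose each visit falls 0 to 0.5 month late, a range suggested by the two-week extension under Plan for Fidelity Monitoring, with v0 = 100, v1 = 4, c = 0, s = 100. The correlated model with one residual then reaches rank 4. At 4 × 47 = 188 participants, the standard errors are about 419 for v0 and 17 for v1; at the 121 randomized, about 559 and 23. With scatter of ±0.5 month they are about 196 and 8.7 (188), or 251 and 11.2 (121). None of these is informative.

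**The case against.** The strongest reply is that non-identification here does no harm to inference. All parameter sets on the ridge give the same marginal covariance matrix, and the likelihood, arm contrasts and their standard errors depend on the random effects only through that matrix. This stands. A reader might infer that standard errors for every 6-month outcome depend on software defaults. They do not; they change only where a simplification restricts the marginal covariance.

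A reader might also infer that a single slope ties the 3-month effect to the 6-month effect. It does not, because the arm and arm-by-time terms fit all eight cells.

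Independent random effects with one residual would be just identified. True, but the plan states neither choice and writes two residuals.

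The splines are only exploratory, and time since enrollment varies between people, so software might return a fit. That fit would rest on the scatter in visit dates alone.

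Finally, the update analyses 3-month outcomes only, so section 1.1 may be obsolete. That limits the practical weight of the point, but the document never says so. Nor does section 3.1 cite 1.1: it cites 2.0, so carrying the problem over to the patient-centered outcomes is an inference from a faulty cross-reference.

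**Conclusion.** The point holds as one about specification and estimand, for secondary outcomes only. At the scheduled visits the model as written has 5 variance parameters (4 with independent random effects) against 3 moments. The components are not identified, the two residuals are never separable, and splines in time are not estimable. The likely consequences are non-convergence or an unplanned simplification of the variance structure. Treatment contrasts at 3 and 6 months are not lost, and the documents do not support the stronger reading that the 6-month comparisons cannot be made.

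The slope has the more direct effect on interpretation: read as the text directs, it would show no benefit for an arm that improved by month 3 and stayed there.

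The ranks assume nominal visit times and change from baseline as the response, as in the equation. With raw scores at 0, 3 and 6 months and one residual, correlated random effects would be identified (4 parameters, rank 4), but that is not the written model. The primary 3-month analysis is unaffected. This should be corrected if the 6-month outcomes are still to be reported.

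**What to change.** State whether the 6-month secondary outcomes still stand.

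- **If they do:** replace the model in 1.1 with a repeated-measures model. The response is the score at 3 and 6 months. Fixed effects are visit as a category, arm, arm-by-visit, and baseline score by visit; the within-person covariance is unstructured. Report the arm contrast at each visit instead of a time slope. Delete the random slope, the second residual and the splines. Correct the cross-reference in 3.1 from section 2.0 to this model.
- **If the update dropped them:** withdraw 1.1 and 3.1 explicitly.

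The unstructured covariance has three parameters for three moments, so nothing is left to software choice. The update already adjusts the 3-month analysis for the baseline measure, so this would bring the 6-month analysis into line. The cost is wording only, with no new data.

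### Section 1.1 names the time coefficient as the change associated with CT, ET and CT+ET, but in the printed model that coefficient is a background slope, not an intervention effect

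*Combined protocol and SAP*

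**What the plan says.** Section 1.1 (Change in Secondary Measures of Cognitive Function Over 6 Months) plans a linear mixed model with a random intercept and a random slope. It starts simply: "We will construct a base model by fitting a single slope after enrollment". It then says which estimate is to be read: "The estimate for the time since enrollment variable will quantify the magnitude of the change in executive and global cognitive function", with the qualifier "pre- and post-intervention) associated with CT, ET, and CT+ET". Cubic splines in time may be explored.

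The equation that follows has change from baseline on the left. Its fixed part contains an intercept, a time term, an intervention term and an intervention-by-time term. The symbols are explained only as follows: "where time is time since enrollment, and X is the vector of interventions". The coding of X is not given.

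Two other places bear on this:

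- The Secondary Objectives set the comparison as "among those receiving CT, ET, or CT+ET relative to those in SC".
- Section 3.1, on patient-centered outcomes over 6 months, says these will be "analyzed using the analytic plan described in 2.0 for repeated measures of executive function". Section 2.0 covers ESRD-specific clinical outcomes (mortality, dichotomous and count outcomes) and contains no repeated-measures plan. The only such plan is in Section 1.1.

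**The concern.** The sentence in Section 1.1 assigns the intervention result to a term that carries no information about arm. Followed literally, it would report a trend over time as change associated with the interventions. That replaces the randomised comparison with a before-after one.

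The difference matters here because the protocol's own background expects cognition to decline on hemodialysis, so a zero background slope cannot be assumed. A declining background could be read as harm or lack of benefit in the active arms. A stable background could hide a real difference between arms. Section 1.0 writes out its arm contrasts for the 3-month analysis; Section 1.1 writes out none, so this sentence is the only place in that section that names the estimate to be read. If Section 3.1 was meant to point to Section 1.1, the same sentence would also govern the 6-month patient-centered outcomes.

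**Working it through.** The plan gives no figure for this analysis, so there is none to reproduce. The check is algebra on the printed model, followed by a simulation with assumed slopes.

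**Algebra.** The fixed part of the printed model, at month t, is

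E(change | X, t) = β00 + β1·t + β01·X + β11·X·t.

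- Slope over time: β1 + β11·X.
- If X = 0 denotes SC (an assumption), SC has expected change β00 + β1·t and slope β1. The time coefficient is then the SC slope.
- An active arm minus SC at month t: (β00 + β1·t + β01 + β11·t) − (β00 + β1·t) = β01 + β11·t.

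β1 cancels from the comparison with SC. The time coefficient is printed with a subject index, which looks like a notation slip because the random slope is listed separately; it does not change this result.

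**Simulation.** Assumed monthly slopes, not from the documents: SC −1.0, CT 1.0, ET 1.5, CT+ET 2.0, with no arm difference at time 0. The true slope differences from SC are therefore 1.0 − (−1.0) = 2.0, 1.5 − (−1.0) = 2.5 and 2.0 − (−1.0) = 3.0. The average slope over the four arms is (−1.0 + 1.0 + 1.5 + 2.0)/4 = 0.875. The fixed effects were fitted by least squares with 4,000 per arm, and a mixed model with random intercept and slope was fitted with 150 per arm.

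| Model and coding | Visits (months) | Time coefficient | What it estimates |
|---|---|---|---|
| Arm indicators, SC = 0 | 0, 3, 6 | −0.99 | SC slope |
| Arm indicators, SC = 0 | 3, 6 | −1.01 | SC slope |
| 0/1 factorial coding | 0, 3, 6 | −0.99 | SC slope |
| 0/1 factorial coding | 3, 6 | −1.01 | SC slope |
| Effect coding (±0.5) | either set | 0.88 | average over arms |
| Single-slope base model | either set | 0.88 | average over arms |
| Mixed model, arm indicators | 0, 3, 6 | −1.06 | SC slope |

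The arm-by-time coefficients (arm indicators; visits 0, 3, 6) were 2.00, 2.49 and 3.01, against true values of 2.0, 2.5 and 3.0. The mixed model gave 2.04, 2.57 and 3.07. Under 0/1 factorial coding the CT+ET difference is the sum of three terms: 2.00 + 2.49 − 1.48 = 3.01.

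So the printed model can deliver the arm comparisons, but through the X and X-by-time terms. The coefficient that the sentence names does not deliver them under any of these codings. With splines, time is carried by several terms, so no single time estimate remains to be read; a contrast at 3 or 6 months is still defined.

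**The case against.** The strongest reply is that the later statistical update, prompted by the COVID-19 shutdowns, describes a different analysis. It places primary and secondary outcomes at 3 months and analyses change by linear regression and ANCOVA, with SC as comparator. It mentions no mixed model and no 6-month slope, and it records that the trial was terminated. This stands as a limit on practical reach. It does not settle the point, because the update does not expressly withdraw Section 1.1 or the 6-month secondary outcome.

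A second reply is that the Secondary Objectives already name SC as comparator, that the equation contains the terms needed to compare arms, and that a competent analyst would use them. That is likely, and it makes the fault one of wording rather than of model. Even so, a plan that names an estimate should name the right one.

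A reader might infer more than the documents support in four ways:

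- *That the coefficient simply is the SC slope.* That needs X = 0 for SC, which is natural but not written. The sentence also comes between the single-slope base model and the full equation, and in the base model the coefficient averages over arms.
- *That a bias in Trail Making seconds can be stated.* Change in Trail Making at 3 months is the primary outcome and falls under Section 1.0. Moreover, β1 is a rate per unit time, and expected SC change also includes β00, so β1 alone does not give even the SC change at a visit.
- *That the arm-by-time coefficient alone would be wrong.* It is a valid contrast of slopes. It is incomplete as the effect at a visit only when β01 is not zero.
- *That Section 3.1 certainly inherits the fault.* Its reference is to Section 2.0; that Section 1.1 was meant is an inference.

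**Conclusion.** The point holds as a misnamed estimate in Section 1.1. The time coefficient describes background trend: the SC slope if SC is the zero level of X, or the average slope over arms under effect coding or in the base model. It is not the effect of CT, ET or CT+ET under any coding examined, and one number cannot be three arm effects.

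The size of the resulting error cannot be given from the documents, since it depends on the background slope. The simulated values rest on assumed slopes and show only that the two quantities can differ in sign as well as size.

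The reach is limited to the secondary longitudinal analyses over 6 months: cognitive measures under Section 1.1 and, if the cross-reference was meant for it, patient-centered outcomes under Section 3.1. A reader might conclude that the trial's main result is at risk. It is not: the primary 3-month analysis in Section 1.0 and the regression and ANCOVA in the update do not use this coefficient.

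**What to change.** Do one of the following before any 6-month result is reported.

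1. If Section 1.1 still applies, replace the sentence. State that the intervention effect for each arm against SC is β01 + β11·t from the printed model, evaluated at t = 3 and t = 6 months with 95% CI, or the equivalent contrast if splines are used. State the coding of X; if it is factorial, say that the CT+ET contrast sums the CT, ET and interaction components. Add that the time term alone describes background trend. The continuous-time model can stay as printed.
2. If the 3-month regression and ANCOVA in the update replace this analysis, say that Section 1.1 is withdrawn and what becomes of the 6-month secondary outcome.

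In either case, correct the reference in Section 3.1. If Section 1.1 was meant, the same contrast (or the same withdrawal) then applies to the patient-centered outcomes.

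The cost is a few sentences of text. No new data and no different model are needed, since the contrasts come from the model already specified.
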